6.1 Supervised Exercise Plan (Cycles 0-11)

The exercise intervention will include 48 weeks of aerobic and resistance training three times per week with the goal of delivering three moderate-to-vigorous aerobic training sessions and two structured resistance training sessions each week. A total of 88 supervised sessions should be completed within Year 1, in the event that the patient does not have any AEs that would prohibit him from reducing the number of exercise sessions. As long as the prescribed supervised dose is 88 sessions in Year 1, there is flexibility regarding the number of supervised sessions in a given week in Year 1.

Original Program: We strongly advise patients to adhere to the original program, with patients receiving three supervised exercise sessions in weeks 1-4 (Cycle 0), prior to the supervised exercise sessions tapering

throughout the program to two supervised sessions and one self-managed session for weeks 5-36 (Cycles 1-8) and one supervised training session and two self-managed sessions for weeks 37-48 (Cycles 9-11).

Flexible Entry: Although patients randomised to Supervised Exercise are **requested** to complete 3 supervised exercise sessions per week during Cycle 0 (totalling 12 supervised exercise sessions in this cycle), we recognise that some patients may require an 'easier' entry into the study in order to agree to enrol. This **flexible entry** option is permitted, where patients may complete a minimum of 1 to a maximum of 3 supervised sessions each week in Cycle 0, prior to joining the 'full program' from Cycle 1 onwards. However, while we allow the flexibility of less than 3 supervised sessions per week, those sessions will need to be made up later in Year 1 such that they complete the 88 sessions within Year 1. If using a flexible entry option, please prioritise the combined high-intensity interval training and resistance training sessions (Day 1 or Day 3 above) as it is easier to insert moderate-intensity continuous training sessions (Day 2) later in the program, when recovering missed supervised sessions. Examples of flexible entry plans are included in the SOM.

Exercise prescription will be tailored to the participant's baseline cardiopulmonary and strength assessments, and baseline conditions. The three training sessions each week will be **generally** structured as follows, with subtle alterations for variety, periodisation **and autoregulation**:

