6.1.8 Behavioural Support Program (Intervention Arm Only)

Participants will be asked to complete at least one unsupervised exercise session per week (hereafter referred to as self-managed exercise) starting in Week 5 (Cycle 1). The more self-managed exercise the participants are asked to engage in, the more behavioural support will be provided. The behavioural support will be provided utilizing text messages rooted in constructs/strategies from Social Cognitive Theory (SCT) and the Theory of Planned Behaviour (TPB). The overarching focus of the behavioural support will be to increase/enhance perceived control in task-specific exercises and overcoming individual barriers to exercise. The behavioural support provided will be encompassing, consistently delivered, and provided to each participant throughout the program. There will be four 'levels' of behavioural support ([Table 4](#)):

1. [3x/week supervised \(cycle 0\)](#)

2. 1x/week self-managed; 2x/week supervised (cycles 1-8)
3. 2x/week self-managed; 1x/week supervised (cycles 9-11)
4. Totally self-managed; 1x/cycle supervised (cycles ≥ 12)

Table 4. Guidelines for Level of Behavioural Support

Level of Self-Management	Behavioural Support Components
No self-management 3x week supervised Cycles 0	The behavioural support will focus on: 
 ○ Perceived competence ○ Identifying and overcoming barriers to exercise ○ Goal setting ○ Enhancing self-efficacy 
 ➤ 1x per week pt. would get a text message/e-mail emphasising one of the topics above “signed” by the exercise specialist. Each week would be a different message working “down” off the list
1x week self-managed; 2x week supervised Cycles 1-8	The behavioural support will focus on: 
 ○ Perceived independence ○ Securing social support ○ Maintaining/enhancing self-efficacy ○ Identifying and overcoming barriers to exercise ○ Self-monitoring ○ Goal setting 
 ➤ 2x per week pt. would get a text message emphasising 2 of the topics above “signed” by the exercise specialist – each week would be a different pair working “down” off the list.

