13.1 Definitions

13.1.1 Clinical Adverse Events (AE)

A clinical adverse event is any unfavourable or unintended sign, symptom, or disease temporally associated with the study intervention and occurring in a patient assigned to the intervention. All AEs reported from the date of informed consent until 28 days after the Off-Study visit will be considered. AEs are assessed by the exercise physiologist, trainer, etc. at on-site exercise visits and in all subjects (in person or by phone) on a monthly basis. This includes adverse clinical or laboratory findings, illness, or an exacerbation or progression of a disease/condition present at baseline. A list of standard questions will be used to assess any AEs, provided in the SOM.

In this trial, the study intervention is defined as supervised aerobic and resistance exercise. All potential participants will be screened via their medical charts as well as through in-person assessments to assess cardiovascular contraindications to exercise. Our multi-gated comprehensive approach should systematically identify and screen out any individual for whom this study is contraindicated.

However, rare but serious AEs are possible. Those that may occur during either cardiopulmonary exercise testing (CPET) or exercise training include myocardial infarction (heart attack), stroke, unconsciousness or other serious injury.

- Events during a CPET are rare (<1/100,000 in well individuals and 1/10,000 in sick individuals). A trained health professional (e.g. medical staff and exercise physiologist) will monitor the exercise test in a location staffed by physicians, in the rare event that such an event occurs.
- Similar to a CPET, exercise training may cause temporary risks of an adverse cardiovascular event, such as a heart attack. The CPET with ECG-monitoring that must be completed prior to randomisation will ensure that all randomised participants are healthy enough to engage in exercise training.

Absolute and relative indications for stopping exercise (both testing and training) are provided in [Table 5](#). In the event of a participant presenting with any of the below symptoms exercise should be stopped.

Table 5. Indicators for Stopping Exercise

Absolute indications for Stopping Exercise:

- Suspicion of a myocardial infarction or acute myocardial infarction (heart attack)
- Onset of moderate-to-severe angina (chest pain)

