13.3 Attribution

A suspected adverse reaction means any adverse event for which there is reasonable possibility that the intervention caused the adverse event. For the purposes of safety reporting, “reasonable possibility” means there is evidence to suggest a causal relationship between the intervention and the adverse event.

The Investigator will assign attribution of the possible association of the event with the study intervention using the following definitions:

Unrelated to the exercise intervention: The adverse event is *Unlikely* or *Not Related* to the exercise intervention

Related to exercise intervention: The adverse event is *Possibly*, *Probably*, or *Definitely* related to the exercise intervention.

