13.5.2 Reporting Deaths

Regardless of relationship to the exercise intervention, all deaths on study should be reported through and including 28 days after the end of the Off-Study visit. Deaths occurring after this period do not have to be reported as SAEs unless considered related to the exercise intervention. For all SAEs, the Investigator is obligated to pursue and provide information to the SCC in accordance with the timeframes for reporting specified above. In addition, an Investigator may be requested to obtain specific additional follow-up information in an expedited fashion. This information may be more detailed than that captured on the AE CRF. In general, this will include a description of the adverse event in sufficient detail to allow for a complete medical assessment of the case and independent determination of possible causality. Information on other possible causes of the event, such as concomitant medications and illnesses must be provided. In the case of a patient death, a summary of available autopsy findings must be submitted as soon as possible to the Study Coordination Centre.

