13.7 Statistical Analysis of Adverse Events

Adverse event rates will be summarised with frequency and percentage within each arm and across arms. Rates between groups will be compared using the intention-to-treat approach. In addition, AE incidence rates will be summarised by severity and relationship to the intervention. Intervention-related AEs are those judged by the Investigator to be at least possibly related to the intervention. Adverse events with missing severity or relationship to the intervention will be classified as severe and treatment-related, respectively. Patients with multiple occurrences of events will only be counted once at the maximum severity for each preferred term, SOC, and overall. Deaths that occur within 28 days after the 24th cycle clinic visit are defined as on-study deaths.

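### Section 13.1.1 limits the study intervention to supervised exercise, in conflict with Sections 6.1, 12.2 and 13.3, so relatedness of events from self-managed sessions and study tests is not clearly defined

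*Combined protocol and SAP*

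**What the plan says.** The definition stands in the safety section, under clinical adverse events (13.1.1): "In this trial, the study intervention is defined as supervised aerobic and resistance exercise". The same section defines an adverse event by its timing relative to the study intervention and by its occurrence in a patient assigned to that intervention.

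Section 13.3 speaks of "evidence to suggest a causal relationship between the intervention and the adverse event" and asks the investigator to judge association with the study intervention. The two categories offered are related or unrelated to the *exercise* intervention, and Section 13.0 uses that same term for the form item. Section 13.7 then says that "AE incidence rates will be summarised by severity and relationship to the intervention".

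Elsewhere the intervention is wider:

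- Section 6.1: "The exercise intervention will include 48 weeks of aerobic and resistance training three times per week", with self-managed sessions scheduled from week 5. Of the Year 1 sessions, "A total of 88 supervised sessions should be completed within Year 1".
- Section 6.1.4: the intervention period runs until Cycle 24.
- Section 6.1.8: "Participants will be asked to complete at least one unsupervised exercise session per week" from Cycle 1, and from Cycle 12 the programme is "Totally self-managed; 1x/cycle supervised".
- Section 12.2: 12 cycles of supervised exercise are followed by 12 of self-management.

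CPET, 1RM strength tests and the 400 m walk are done in both arms (Section 5.2, Table 1). The first CPET precedes randomisation (Table 1, footnote 4).

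**The concern.** Two terms of different scope govern one field on the adverse event form. An investigator who follows the explicit definition in 13.1.1 would call a fracture in a prescribed self-managed session unrelated. One who follows the category wording in 13.3 would call it related. Both can point to the protocol, and in a multicentre trial whose investigators know the allocation (Section 4.6) the choice may differ by site.

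What is at stake is the relatedness label and what is built on it: the related-event summary in 13.7, and notification to those ethics committees that, according to Section 17.2, ask only for serious, unexpected events judged related to the study intervention. The sessions in doubt are those done without a professional present.

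Study tests raise a second difficulty. Section 13.1.1 itself names heart attack and stroke as possible during CPET. Yet 13.3 offers only relatedness to the exercise intervention, and a man in Arm B has none. At the screening CPET nobody has yet been assigned to anything.

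**Working it through.** **1. Reproduce the plan's own figure (Section 6.1).** Supervised and self-managed sessions in Year 1:

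- Cycle 0, 4 weeks: 3 × 4 = 12 supervised, 0 self-managed.
- Cycles 1–8, 32 weeks: 2 × 32 = 64 supervised, 1 × 32 = 32 self-managed.
- Cycles 9–11, 12 weeks: 1 × 12 = 12 supervised, 2 × 12 = 24 self-managed.

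Supervised: 12 + 64 + 12 = 88, which matches the stated total. Self-managed: 32 + 24 = 56. All sessions: 3 × 48 = 144. Share outside the literal definition: 56 / 144 = 38.9%.

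**2. Extend to 24 cycles.** Cycles 12–23 are 12 × 4 = 48 weeks with one supervised session per cycle (Section 6.1.8), so 12 supervised. The documents give no session count for this period; Section 6.1.4 sets a weekly target of 75 vigorous aerobic minutes and two resistance sessions. Three a week is a reasonable assumption, because the Year 1 pattern in Section 6.1.2 gives 20 + 35 + 20 = 75 minutes over three sessions. Two a week is the lower case, since two resistance sessions are required.

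- Three a week: 3 × 48 = 144 sessions, less 12 supervised = 132 self-managed. Share: (56 + 132) / (144 + 144) = 188 / 288 = 65.3%.
- Two a week: 2 × 48 = 96 sessions, less 12 = 84. Share: (56 + 84) / (144 + 96) = 140 / 240 = 58.3%.
- For sensitivity, four a week: 4 × 48 = 192 sessions, less 12 = 180. Share: (56 + 180) / (144 + 192) = 236 / 336 = 70.2%.

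**3. Compare the attribution texts.** The term in force differs by place:

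- 13.1.1, definition: supervised exercise only.
- 13.3, lead-in: study intervention, the narrowly defined term.
- 13.3, the two categories, and 13.0, the form item: exercise intervention, with no mention of supervision.
- 13.7: the intervention, unqualified.

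The narrow and wide readings therefore meet inside 13.3 itself, and nothing says which governs.

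**4. Check the study tests.** For a test injury in Arm B, neither the narrow nor the wide reading gives a fitting category, because that arm receives no exercise intervention. For an event at the screening CPET, the adverse event definition is not met on its wording, although reporting starts at consent (13.1.1; Table 1, footnote 14). The event is recorded, but the form cannot show that a study procedure may have caused it. Comparing total event rates by arm does not bring this out, because tests common to both arms tend to cancel in the difference.

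**The case against.** The strongest reply is that the operative wording is already wide enough. The categories an investigator ticks, and the form item, say exercise intervention, and Section 6.1 puts self-managed sessions inside that term. *Supervised Exercise* is also the name of the arm, which it keeps through Cycle 24, so the sentence in 13.1.1 may simply mean the exercise given to that arm. The same section speaks of events during exercise training without restricting it to supervised sessions. This stands to the extent that the text is ambiguous: it does not force a self-managed event to be coded as unrelated. It does not remove the conflict, because 13.1.1 gives an explicit definition and the lead-in of 13.3 uses the term so defined.

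Three stronger readings might be inferred, and the documents do not support them.

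- *That harm is under-counted or lost.* Adverse events are sought monthly in all subjects (13.1.1), listed for self-managed days (5.5.6, 5.5.7), recorded whatever their source (13.5) and compared by randomised arm (13.7). A missing relationship counts as treatment-related. Only the label is at risk, although the missing-data rule does not help when the field has been completed as unrelated.
- *That 58–65% of exercise-related events fall outside the definition.* That would require events to be proportional to sessions. In Cycles 1–8 the self-managed day is continuous aerobic work only, while both supervised days combine resistance with interval training (5.5.6), so proportionality is doubtful, and no event data are given.
- *That late deaths escape reporting.* Section 13.5.2 says: "Deaths occurring after this period do not have to be reported as SAEs unless considered related to the exercise intervention". That is the wider term, so the narrow definition does not clearly reach it.

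**Conclusion.** The plan is wrong as written on a narrow point: the stated definition of the study intervention contradicts its own description of the exercise programme, and attribution in 13.3 draws on both. Read literally, the definition omits 39% of prescribed sessions in Year 1. Over 24 cycles it omits about 58–65%, assuming two to three sessions a week continue in Year 2 with one supervised per cycle. The Year 1 figure follows from the document; the 24-cycle figure rests on that assumption.

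The consequence is possible, not demonstrated: relatedness may be coded inconsistently between sites, and related events may be under-counted in the 13.7 summary. The comparison of all events by arm does not depend on the label.

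The study-test gap is smaller but does not depend on how the definition is read. CPET, 1RM and 400 m walk events in Arm B, and events at the pre-randomisation CPET, have no fitting category, although they are recorded.

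**What to change.** - In 13.1.1, define the study intervention as all protocol-prescribed aerobic and resistance exercise in Arm A, whether supervised or self-managed. Use that single term in 13.3, 13.5.2 and 13.7, and for the form item in 13.0.
- Amend the adverse event definition in 13.1.1 so that it covers both arms from informed consent, not only patients assigned to the intervention.
- In 13.3 and on the adverse event form, add a separate attribution for both arms: related to a study exercise test. Report it in 13.7.
- Reconcile the statement in Section 16.2 that a certified professional supervises every session with the self-managed sessions in Section 6.

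A table of related events in Arm A by supervised or self-managed setting is optional.

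The cost is a few sentences, one more field on the adverse event form, and a review of the relationship field for events already coded. No visits or assessments are added.

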13.1.2 Serious Adverse Events (SAE)

A serious adverse event (SAE) is any adverse event occurring at any level of intervention that results in any of the following outcomes:

- Results in death. *If the malignancy under study has a fatal outcome during the study or within the safety reporting period, the event leading to death should be reported as a Grade 5 SAE; death is an outcome and not the adverse event in itself.*
- Is life-threatening (i.e., immediate risk of death from the reaction as it occurred). *It does **not** include a reaction which hypothetically might have caused death had it occurred in a more severe form.*
- Requires or prolongs inpatient hospitalisation (i.e., the event required at least a 24-hour hospitalisation or prolonged a hospitalisation beyond the expected length of stay). Hospitalisation admissions and/or surgical operations scheduled to occur during the study period, but planned prior to study entry are not considered SAEs if the illness or disease existed before the person was enrolled in the trial, provided that it did not deteriorate in an unexpected manner during the trial (e.g., surgery performed earlier)
- Results in persistent or significant disability/incapacity. Disability is defined as a substantial disruption of a person's ability to conduct normal life functions
- Results in a congenital anomaly or birth defect
- Is an important medical event when, based upon appropriate medical judgment, it may jeopardise the participant and require medical or surgical intervention to prevent one of the outcomes listed above.

Events **not** considered to be SAEs are hospitalisations for:

- Routine treatment or monitoring of the studied indication, not associated with deterioration in condition
- Elective or pre-planned treatment for a pre-existing condition that did not worsen
- Emergency outpatient treatment for an event not fulfilling the serious criteria outlined above and not resulting in inpatient admission
- Respite care or social admissions

13.1.3 Non-Serious Adverse Events

All other events.

13.2 Expectedness

An adverse event or suspected adverse reaction is considered “unexpected” if it is not listed above or included in the following list:

Bone pain, pathological skeletal fracture
Musculoskeletal injury (sprain, strain)
Joint pain
Falls
Muscle soreness

13.3 Attribution

A suspected adverse reaction means any adverse event for which there is reasonable possibility that the intervention caused the adverse event. For the purposes of safety reporting, “reasonable possibility” means there is evidence to suggest a causal relationship between the intervention and the adverse event.

The Investigator will assign attribution of the possible association of the event with the study intervention using the following definitions:

Unrelated to the exercise intervention: The adverse event is *Unlikely* or *Not Related* to the exercise intervention

Related to exercise intervention: The adverse event is *Possibly*, *Probably*, or *Definitely* related to the exercise intervention.

13.4 Severity

Signs or symptoms should be graded and recorded by the Investigator according to the National Cancer Institute’s Common Terminology Criteria for Adverse Events (CTCAE) Version 4.0 (SOM: [Appendix 30](#)). When specific adverse events are not listed in the CTCAE, they are to be graded as mild, moderate, severe, or life-threatening according to the following grades and definitions:

Table 6. AE Severity Grading

Severity (Toxicity Grade)	Description
Grade 1	Mild; asymptomatic or mild symptoms; clinical or diagnostic observations only; intervention not indicated
Grade 2	Moderate; minimal, local or non-invasive intervention indicated; limiting age- appropriate instrumental activities of daily living (ADL)
Grade 3	Severe or medically significant but not immediately life-threatening; hospitalisation or prolongation of hospitalisation indicated; disabling; limiting self-care ADL
Grade 4	Life-threatening consequences; urgent intervention indicated
Grade 5	Death related to AE

13.5 Reporting Requirements

All AEs and SAEs whether reported by the patient, discovered during questioning, directly observed, or detected by physical examination, laboratory test or other means must be recorded in the patient’s medical record and on the AE form in the online study database. All AEs should be reviewed by the site PI. The Investigator is responsible for notifying the Institutional Review Board/Independent Ethics Committee (IRB/IEC) about AEs in accordance with local regulations.

13.5.1 SAE Reporting

At screening, the reporting period for SAEs begins from the time the patient provides informed consent and prior to the patient's participation in the study, i.e., prior to undergoing any study-related procedure through and including 28 days after the Off-Study visit. All SAEs occurring during the study must be reported to the site PI by study-site personnel within 24 hours of their knowledge of the event. This timeframe also applies to additional new information (follow-up). SAEs will be reported via a study supplied SAE form and sent to the SCC, to be reviewed by the data safety and monitoring committee, within 24 hours of site PI awareness. The names (and corresponding telephone numbers) of the individuals who should be contacted regarding safety issues or questions regarding the study will be provided as a separate document. The Investigator is also responsible for notifying the Institutional Review Board/Independent Ethics Committee (IRB/IEC) in accordance with local regulations. All events should be followed to their resolution, until the Investigator assesses them as stable, irreversible, or until the patient is lost to follow-up, whichever comes first.

